10.0 Setting

- 10.1 The retrospective data analysis will be conducted in building HSBS2 using secured computers provided by UH-College of Pharmacy. The PI and research assistant will have access to the data.
- 10.2 The phone calls will be made on the premises on Cigna HealthSpring under the supervision of the research team at Cigna HealthSpring. The data will be de-identified at Cigna Healthspring and shared with UH through secured servers.
- 10.3 A letter of support from Cigna HealthSpring is attached to the email.

11.0 Risks to Subjects

- 11.1 This study does not involve more than Minimal Risk for the safety of patients.
- 11.2 The intervention participation is completely based on the patients consent, and they are made aware of the same. They can withdraw or choose to stop the call at any point, which is also read out to them. The students making the calls are pharmacy students who have completed human subjects' research training as well as training for motivational interviewing. Additionally, the research team members closely supervise the pharmacy students to ensure the quality of the calls. Thus, it is not anticipated that the intervention can harm any patient in any way

12.0 Potential Benefits to Subjects

- 12.1 Describe the potential benefits that individual subjects may experience from taking part in the research. Include as may be useful for the IRB's consideration, the probability, magnitude, and duration of the potential benefits.
- 12.2 As mentioned in the initial sections of this IRB protocol, medication adherence is very important for patients with comorbid conditions and the lack thereof is an important problem being faced in the real world settings. This intervention uses motivational interviewing, which has successfully been used to improve patient adherence in various other chronic diseases, by helping the patients find their own internal motivation to change and find ways to address their adherence barriers. The intention of this study is to bring about a change in the behavior of patients and to improve their adherence, with a goal to improve the outcomes associated with the disease.

13.0 Withdrawal of Subjects

- 13.1 There is no more than minimal risk for the subjects. There are therefore, no foreseeable circumstances which require withdrawal of subjects. However, the participant can voluntarily refuse to participate in the follow up calls even if they have participated in the first call.

14.0 Costs/Payments to Subjects

N/A. No compensation to the participating patients

15.0 Confidentiality

The intervention will occur on the premises of Cigna Healthspring. No identifiable data will leave the premises. Only encrypted, de-identified data will be available to [name] at UH. There will be no audio recording of the intervention. Only the research team operating from Cigna Healthspring will have access to identifiers.

The UH Pharmacy students who will conduct the intervention will only interact with the patients to conduct the intervention over the phone and will not be able to access any information on the patients otherwise. The students will collect notes about the phone calls to identify number of successful calls, number of attempts made to contact each patient, and barriers to adherence for the successful calls. These notes will be made in a single excel sheet which will be available only at Cigna – HealthSpring. The students will have no access to the notes otherwise. After the completion of the intervention phase, the excel sheet will be deidentified, and will contain a de-identified ID and corresponding barrier to adherence. This information will be provided to UH for understanding the success of the intervention process.

16.0 Provisions to Protect the Privacy Interests of Subjects

- 16.1 The retrospective data analysis will be completely de-identified. For phase two, the personnel making the phone calls will be provided the list of names and numbers to contact at the premises of the health plan for intervention

A motivational interviewing intervention customized by patient adherence patterns (NCT03985098) – 03.28.2018

implementation. During the follow up calls, the patients would be asked if they are willing to participate in the follow up. The students are trained to conduct training using MI to promote behavioral change in a collaborative supportive manner.

- 16.2 After the completion of the intervention stage, post intervention data will be de-identified and the analysis completed. Data will be stored on a secured server for a period of 3 years after completion of the study. The attached script is an example of how MI has been used previously by pharmacy students at UH, in research led by the PI.

17.0 Informed Consent Process

The intervention is conducted on the phone, and therefore the consent will be obtained orally on the phone. The pharmacy student will read the consent letter (attached) to the patient, and once the patient says that he or she agrees to participate in the study, does the student proceed with the intervention. The patient can refuse, or ask the pharmacy student to call another time.

18.0 Process to Document Consent in Writing

The research involves no more than minimal risk of harm to subjects and involves no procedures for which written consent is normally required outside of the research context. The intervention involves only a phone call to educate the patient about adherence. A waiver of obtaining consent in writing is being sought.

19.0 HIPAA

The direct identifiers will be removed before providing any information to University of Houston. All information will be analyzed and results reported in aggregated form. Thus, the protected health information of patients will not be accessed by UH, and therefore we will not be obtaining, creating, using, and/or disclosing individually identifiable health information associated with a HIPAA-covered component or entity in the course of the research.

20.0 Data Management

- 20.1 The data which will be provided by Cigna will contain data with encrypted patient IDs. The electronic data files for this study will be processed on a dedicated, layered-security server, which can be accessed only by [name] and designated project staff members who are under the direct supervision of [name]. Since the system is behind multiple firewalls, is monitored regularly, and is accessible only to key personnel, the risk of unlawful penetration is not a significant data safeguard concern. Data will be stored on the secure server for 3 years following the completion of the study. All analysis will be conducted on the desktop at UH College of Pharmacy. The data will not be accessible through any personal computers.

SAS 9.4 is the statistical software, which will be used for the analysis.

A motivational interviewing intervention customized by patient adherence patterns (NCT03985098) – 03.28.2018

Baseline characteristics: Comparisons in baseline characteristics will be made between the 2 study groups (intervention vs. control) using t-tests for continuous variables and chi-square tests for categorical variables. The characteristics evaluated will include predisposing factors: demographics, and number of other medications used; enabling factors: health plan (LIS vs. not), prescriber specialty (specialist vs. primary care); need factors: comorbidities (CHF, MI, CAD, stroke, ESRD, depression), previous hospitalization and CMS risk score.

Baseline PDC in the 12 months prior to intervention and patient past adherence trajectory will also be compared between 2 groups. Because of the randomization, we do not anticipate any significant differences between the two study groups on these characteristics.

Outcome analysis: Refill data during 2 time periods -- 6, and 12 months, following the initial call of the intervention will be evaluated to calculate adherence rates for both the intervention and control groups. The two periods were chosen to evaluate the intervention effect during the 6 months when the follow up calls were ongoing as well as after these calls had stopped. The adherence rate will be defined as proportion of days covered (PDC) for six and twelve month follow up period following the intervention. An intent to treat analysis will be utilized.

To examine the effect of study group (intervention vs. control) on adherence, study group PDC means for each follow up time, 6 and 12 months, post intervention will be calculated and compared using a t-test. In the event that significant differences in baseline characteristics were observed, multiple regression will be utilized to adjust for the imbalance. The outcome variable will be PDC during each follow up period, 6 and 12 months, following the intervention initial call. The primary exposure variable will be study group, and other covariates will include any baseline characteristics not equally distributed.

Dichotomization of the outcome: Patients in both groups will also be categorized as adherent vs. not during the two follow up periods based on PDC \geq 80% in each time period, 6 and 12 months, to create 2 categorical outcome variables. The effect of study group on adherence will be evaluated for these categorical outcomes using chi-square tests. If significant differences in baseline characteristics were observed, logistic regression models will be utilized to adjust for imbalances

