6.0 Recruitment Methods

LOCAL:

- 6.1 This study will start with the retrospective phase which does not involve recruitment of patients, but involves analysis of existing data. De-identified data will be obtained from Cigna-Healthspring.
- 6.2 The project will be implemented in collaboration with Cigna-Health Spring, a Medicare Advantage Plan in Texas. The health plan has several electronic data files available for analysis including membership file, member

A motivational interviewing intervention customized by patient adherence patterns (NCT03985098) – 03.28.2018

summary file, institutional claims file, professional claims file, quest lab, Cigna-Health Spring's medical claims file (CCMS) and pharmacy file. Pharmacy files contain Part D pharmacy data provided by pharmacy benefits manager including patient/ drug identifying information, fill dates, days of supply, quantity dispensed and dosing for each prescription filled. The refill data will be used to determine the non-adherent patients. ICD-10 codes will be used to determine other exclusions using professional claims data.

Phase 2 will involve project intervention which will be conducted over the phone. A list of actively enrolled members, taking the medication who were a part of phase 1 will be created by Cigna HealthSpring to be used for intervention implementation at their premises. The phone call will be made by University of Houston pharmacy students who will be on rotation at Cigna-HealthSpring. The form of informed consent which will be read to the patient is attached to the IRB. If the patient consents to receive the intervention over the phone, and completes the phone call, the patient forms a part of the intervention group. Five follow-up phones will be attempted one month apart for the patient after the initial call.

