9.3 Phase 2: intervention implementation

Patients that are still enrolled in the health plan during 2017-2018 will be included in phase 2. Patients will be categorized by their adherence trajectory identified in phase 1 and will be randomized to intervention vs. not within each category. The proposed intervention will be a telephone call by a pharmacy student participating in rotations at Cigna-Health Spring Plan and trained in MI and 6 monthly follow up calls. During implementation, students will first examine the patient adherence pattern that was identified in phase 1 which will be coded. The student will then confirm the diagnosis, medication name, and dose with the patient answering the call and will follow the outlined protocol. Using MI, students will assess readiness for change, help patients identify potential barriers in accordance with patient past pattern of use, and guide them to develop a plan to deal with these barriers

A motivational interviewing intervention customized by patient adherence patterns (NCT03985098) – 03.28.2018

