Additionally, the students will ask the 2 questions from the Patient Health Questionnaire (PHQ)-2, a validated screening tool for depression (attached). If the patient responds positively to either question, the student will suggest that the patient schedules an appointment with his/her healthcare provider to discuss these symptoms. The Supervising pharmacists will be available to assist the students in answering any medication related questions that may arise during the calls and arrange for a diabetes educator to contact the patient at a later time if needed. Follow up phone calls will be performed each month for a total of six calls. Students will be supervised by the pharmacist preceptors and managed care pharmacy residents throughout the calls and intervention implementation. The students who will be implementing the calls will attend a three day MI training facilitated by [name], who is experienced in utilizing motivational interviewing to improve adherence. The students will practice calls as a part of their training. They will also complete Human Subjects Research training before their rotation at Cigna Healthspring, and the certificates will be uploaded to the IRB application. After each initial call, students will record the date and write a summary of the interaction with the patient documenting the main barrier/s identified in the conversation and the plan made with the patient. During the follow up calls, students will emphasize the information, confirm problem solved, provide further encouragement and reinforce adherence.

Control group: For every patient that received a call, a control will be randomly selected from the list of patients randomly assigned to the control group.

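### Both PDC windows start at the initial call, which controls and unreached or refusing intervention patients do not have, so the stated intent-to-treat comparison lacks a usable day 0

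*Combined protocol and SAP*

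**What the plan says.** The outcome analysis in Section 20.0 fixes the start of follow-up: "Refill data during 2 time periods -- 6, and 12 months, following the initial call of the intervention will be evaluated". The stated purpose is "to calculate adherence rates for both the intervention and control groups", so one start point is meant to serve both arms. The regression paragraph repeats it: "The outcome variable will be PDC during each follow up period, 6 and 12 months, following the intervention initial call". On the analysis set, Section 20.0 says only: "An intent to treat analysis will be utilized".

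Three other places decide who can have a call date:

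- Section 9.3 sorts patients by adherence trajectory and says they "will be randomized to intervention vs. not within each category".
- Section 6.2 then defines the intervention group by what happens on the telephone: "If the patient consents to receive the intervention over the phone, and completes the phone call, the patient forms a part of the intervention group".
- Section 9.3 builds the control group from completed contact: "For every patient that received a call, a control will be randomly selected from the list of patients randomly assigned to the control group".

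Section 17.0 allows a patient to decline or to ask for a later call. Section 20.0 also compares the arms on PDC over the 12 months before the intervention. No section defines a randomisation date, a calendar date or an assigned date as day 0 for patients who are not called.

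**The concern.** A PDC needs a first and a last day. When that first day is an event that only one arm can experience, the other arm has no window until someone supplies a rule, and the plan supplies none. Two analysts with the same refill file could date controls differently and obtain different primary results.

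Within the intervention arm, the only patients with a completed-call date are those who were reached and agreed. Using the anchor as written means keeping those patients and dropping the rest. That conditions one arm on contact and consent, while controls face no such filter. People who answer the telephone and accept adherence counselling may well refill differently from those who do not, so the randomised comparison would be lost.

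The baseline PDC has the same gap, since its 12 months end at an intervention that controls never receive. The baseline comparisons decide whether the adjusted model is used, so the gap carries through to the choice of analysis.

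**Working it through.** **Step 1. Does the written anchor exist for each type of patient?** Intent to treat is not defined further in the plan; I take its usual meaning, everyone randomised as assigned.

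| Patient | Completed-call date | Retained under 6.2 and 9.3 | Retained under intent to treat (20.0) |
|---|---|---|---|
| Intervention, call completed | Yes | Yes | Yes |
| Intervention, refused | No | No | Yes |
| Intervention, never reached | No | No | Yes |
| Control, drawn for a called patient | No | Yes | Yes |
| Control, not drawn | No | No | Yes |

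Only the first row has a day 0. Four of the five rows belong in the intent-to-treat set without one.

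**Step 2. The plan's own count.** Section 5.2 gives 250 to 300 intervention patients, one control each, and a total of 500 to 600. 2 × 250 = 500 and 2 × 300 = 600, so the total reproduces. Read with the group definition in Section 6.2, these are completed calls plus one control each; patients assigned to intervention but not called successfully are not in the count.

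**Step 3. How many undated intervention patients could there be?** The documents give no completion rate c, so c is an assumption. Undated = n/c − n, with n/c rounded up:

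| c (assumed) | n = 250 | n = 300 |
|---|---|---|
| 0.9 | 278 − 250 = 28 | 334 − 300 = 34 |
| 0.7 | 358 − 250 = 108 | 429 − 300 = 129 |
| 0.5 | 500 − 250 = 250 | 600 − 300 = 300 |
| 0.3 | 834 − 250 = 584 | 1,000 − 300 = 700 |

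**Step 4. What could an arbitrary control date do?** Section 7.4 gives 8 months of enrolment. Assume calls are uniform over it and every control is dated at its start.

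- Mean misalignment = 8/2 = 4 months; only the last patient called is 8 months out.
- Mean calendar overlap of the 6-month windows = (1/8) × (6²/2) / 6 = 18/48 = 37.5%.
- Mean overlap of the 12-month windows = (12 − 4)/12 = 66.7%.
- With an assumed drift of 0.005 to 0.010 PDC a month, mean shift in control PDC = 4 × 0.005 to 4 × 0.010 = 0.02 to 0.04. Its direction depends on whether adherence is falling or rising.

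**Step 5. Context for that shift.** The plan states no SD, power or effect size. Assuming a two-sided 5% test, 80% power and an SD of 0.20 to 0.30, the detectable difference is 2.80 × SD × √(2/n). At SD 0.20 it is 0.050 (n = 250) and 0.046 (n = 300); at SD 0.30 it is 0.075 and 0.069. The illustrative shift is below all of these but not negligible beside them.

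**The case against.** The strongest reply is that the control drawn for each called patient naturally takes that patient's call date, and that under Section 6.2 every analysed intervention patient has one. On that construction nobody analysed lacks a day 0, and the calendar misalignment is zero. Choosing a mid-enrolment date for controls would also bring the net mean shift close to zero.

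Part of this stands. A shared date would align calendar time for drawn controls, so the 0.02 to 0.04 is one scenario and not an expected bias. But the plan never says the date is shared, and the construction works only by leaving out unreached and refusing patients, which contradicts the intent-to-treat statement.

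Four stronger readings might be inferred, and the documents do not support them:

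- *Call dates will be unavailable to the analyst.* The sheet that "will contain a de-identified ID and corresponding barrier to adherence" (Section 15.0) holds call notes sent to help understand the intervention process. It is not described as the only transfer. Section 9.3 has students record the date after each initial call, and Section 16.2 provides separately for de-identified post-intervention data.
- *Called patients are known to be alive and enrolled while controls are not.* Section 6.2 draws phase 2 from active members, Section 9.3 requires continued enrolment, and Section 3.1 excludes deaths and disenrolments without distinguishing arms, though that rule may be meant for phase 1. What mainly remains is the difference in reachability and consent.
- *The shift could reach 0.08.* That applies the maximum misalignment of 8 months to the mean; the mean is 4.
- *Intent to treat is impossible in this trial.* It cannot be run under the written definition, but a short index-date rule would make it possible.

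**Conclusion.** The point holds. The start of follow-up in Section 20.0 exists only for patients who completed a call, so it conflicts with the intent-to-treat statement in the same section. This is more than a missing detail, because the only way to apply the text literally is to select one arm on contact and consent.

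The conclusion rests on the wording alone. The numbers show scale under stated assumptions: a mean control shift of 0.02 to 0.04 if controls are dated at enrolment start, calls are uniform and drift is 0.5 to 1.0 points a month; and anywhere from 28 to 700 undated intervention patients for completion rates from 90% down to 30%. None of the drift, completion rate or SD values comes from the documents. The plan should be changed before outcome data are examined, but nothing here shows that a result is already biased by a known amount.

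**What to change.** Define one index date that exists for every randomised patient in both arms, whether or not contact is made. Two options meet this:

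- the randomisation date; or
- the date of the first scheduled call attempt, with the same date assigned to a control in the same trajectory stratum. The schedule must cover everyone assigned to intervention, including those never reached.

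Use this date as day 0 of the 6- and 12-month PDC windows and as the end of the 12-month baseline PDC, and include it in the de-identified analysis data. Then reconcile Section 6.2 (group defined by a completed call), Section 9.3 (controls drawn per called patient) and Section 20.0 (intent to treat) so that all randomised patients are analysed as assigned.

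Costs: days between the index date and first contact count as follow-up, and unreached patients dilute the effect, so the 250 to 300 per arm should be reconsidered as numbers randomised. The lag matters most if everyone is randomised on one day at the start of enrolment. With uniform calls over 8 months, (8 − 6)/8 = 25% of calls would come after the 6-month window had closed. The scheduled-attempt date avoids most of that lag. Randomising in batches shortly before calling would too, but it is an operational change and is optional. Most of the work is wording and one added data field; no section says that a randomisation date is currently recorded, so that option would mean starting to record it.

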7.0 Study Timelines

- 7.1 The duration of the total study will be 3 years. Retrospective analysis of phase 1 and intervention development will require 12 months. The retrospective analysis will use data from July2016-January 2018. July – December 2016 will be used for baseline covariate measurement. January 2017- January 2018 will include adherence measurement. However this is de-identified patient data used for retrospective analysis and does not require patient participation.
- 7.2 The phase 2 of the study will involve the intervention call provided in the day of consent followed by monthly follow-up calls for six months. The patient however can refuse to participate in any of the calls, even if the patient has completed the primary phone call
- 7.3 The number, frequency and length of study visits: One intervention call lasting 12-15 minutes on average. Monthly follow up calls to the patients who received the initial call for six months lasting on an average for 5-10 minutes.(First call + 5 follow-up calls)
- 7.4 The duration anticipated to enroll all study subjects: The enrollment will continue for a period of 8 months (equivalent to an 2 active semesters)
- 7.5 The estimated date for the investigators to complete this study: 3 years Timeline details below

**A motivational interviewing intervention customized by patient adherence patterns
(NCT03985098) – 03.28.2018**

	Pre-award	Study Period: 36 months																	
		1 2	3 4	5 6	7 8	9 10	11 12	13 14	15 16	17 18	19 20	21 22	23 24	25 26	27 28	29 30	31 32	33 34	35 36
IRB Approval																			
Phase 1 trajectory modeling																			
Intervention Development																			
MI training and randomization																			
Intervention implementation																			
Post intervention analysis																			
Manuscript / Final report prep																			

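### The 12-month PDC includes the 6-month call period, so it cannot show whether the effect lasts after the calls stop, which is the stated reason for measuring it

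*Combined protocol and SAP*

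**What the plan says.** All the relevant text is in section 20.0 of the combined protocol and SAP, under Outcome analysis and Dichotomization of the outcome.

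- **Purpose of the two windows.** They are meant to evaluate the effect "during the 6 months when the follow up calls were ongoing as well as after these calls had stopped".
- **Windows.** The data are "Refill data during 2 time periods -- 6, and 12 months, following the initial call of the intervention", and the adherence rate is "proportion of days covered (PDC) for six and twelve month follow up period following the intervention".
- **Primary comparison.** "study group PDC means for each follow up time, 6 and 12 months, post intervention will be calculated and compared using a t-test".
- **Regression, if baseline imbalance is found.** "The outcome variable will be PDC during each follow up period, 6 and 12 months, following the intervention initial call".
- **Binary outcome.** PDC of at least 80% is assessed "in each time period, 6 and 12 months, to create 2 categorical outcome variables".

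The calls fall in roughly the first six months. Section 7.3 gives "First call + 5 follow-up calls", in line with section 6.2, while section 9.3 refers in one place to six follow-up calls after the first.

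The plan defines no months 7-12 PDC, no contrast between the two half-years and no longitudinal model of PDC after the intervention. The 30-day PDC intervals in section 9.1 belong to the retrospective phase 1 analysis.

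**The concern.** The plan names two questions: does the intervention work while patients are being called, and does it work once the calls have ended? The first has a matching outcome. The second does not, because half of the 12-month window is the call period itself.

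An effect that disappears when the calls stop would still leave a positive 12-month difference. Given the reason the plan states for this window, a significant result would naturally be taken as evidence that the benefit lasts. A reversal after the calls end would be diluted in the same way. Durability matters for a low-cost call programme, and section 2.1 expects benefit for long-term outcomes.

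**Working it through.** **The plan's own figure.** The only phase 2 number is the sample size in section 5.2: 250-300 intervention patients with one control each. 2 × 250 = 500 and 2 × 300 = 600, which matches the stated 500-600. No alpha, power, effect size or SD accompanies it, so there is no power calculation to reproduce.

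**Step 1: what the 12-month PDC measures.** With two equal halves,

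PDC(1-12) = [PDC(1-6) + PDC(7-12)] / 2,

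so the 12-month group difference is the mean of the call-period and post-call differences. Write these as d and e; the 12-month difference is (d + e)/2.

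**Step 2: effect gone after the calls (e = 0).** The 12-month difference is d/2:

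- d = 0.05 gives 0.025
- d = 0.08 gives 0.04
- d = 0.10 gives 0.05

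This step needs no assumption about variance.

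**Step 3: reversal after the calls.** Take d = 0.08 and e = -0.04. The 12-month difference is (0.08 - 0.04)/2 = 0.02, still in favour of the intervention although the intervention group is worse after the calls.

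**Step 4: how often the planned 12-month t-test would be significant when e = 0.** The group sizes come from section 5.2. The rest is assumed: half-year PDC SD of 0.25 or 0.30 (equal in both halves), correlation between halves (rho) of 0.5, 0.7 or 0.9, d from 0.05 to 0.10, and a two-sided 0.05 level.

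- SD of the 12-month PDC = SD × sqrt((1 + rho)/2)
- SE of the difference = that SD × sqrt(2/n)
- Probability of significance ≈ Φ((d/2)/SE - 1.96)

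Example with SD 0.30, rho 0.5, n = 250 and d = 0.08: the 12-month SD is 0.30 × sqrt(0.75) = 0.260, the SE is 0.260 × sqrt(2/250) = 0.0232, and 0.04/0.0232 = 1.72. The probability is Φ(1.72 - 1.96) = 0.41.

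Ranges over rho 0.5-0.9 and n = 250-300 per group:

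| Call-period effect d | SD 0.30 | SD 0.25 | Months 7-12 PDC tested instead |
|---|---|---|---|
| 0.05 | 0.158-0.217 | 0.208-0.293 | 0.05 |
| 0.08 | 0.333-0.470 | 0.450-0.619 | 0.05 |
| 0.10 | 0.481-0.654 | 0.631-0.807 | 0.05 |

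The last column is the test's nominal level, because the expected months 7-12 difference is zero.

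**Step 5: binary outcome.** A patient with PDC 1.00 in months 1-6 and 0.60 in months 7-12 has a 12-month PDC of (1.00 + 0.60)/2 = 0.80. That patient counts as adherent at 12 months although below 80% after the calls stopped.

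**The case against.** The strongest reply has four parts.

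1. **Durability is a rationale, not an aim.** The hypothesis (1.2) and endpoint 8.3 ask whether the intervention improves adherence. PDC over 6 months and over 12 months both address that, and neither comparison is biased by this point. This is correct, and it limits the fault to the post-call question. The plan does, however, give that question as a reason for having two windows.
2. **The rejections are not false positives for 12-month adherence.** A difference of d/2 over the year is real. This also stands: the error lies in reading the test as a post-call result, and the 5% benchmark applies to that reading. The plan sets no such decision rule, but its rationale invites one.
3. **The post-call effect can be recovered.** With equal halves it is about 2 × (12-month difference) - (6-month difference). That works for the means, so a careful reader could detect a fade or a reversal. It is not a planned estimate, it comes with no standard error or test, and it does not work for the PDC of at least 80% outcome.
4. **The sizes rest on assumptions.** They do, which is why ranges are shown. The d/2 result does not depend on them.

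One could also read the rationale as implying a months 7-12 window. No text defines one, and an analyst following section 20.0 would compute PDC over the whole year.

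**Conclusion.** The concern holds. As written, the 12-month outcomes, continuous and dichotomised, do not deliver the post-call evaluation for which the window was chosen. If the effect ends with the calls, the 12-month mean difference is exactly half the call-period difference, given equal halves.

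Under the assumed SDs and correlations, the 12-month t-test would then be significant in about 16-29% of trials for d = 0.05, 33-62% for d = 0.08 and 48-81% for d = 0.10. The percentages are illustrative; the direction is not in doubt.

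The limitation lies in the planned analyses, not in the data, since the refill records can supply a months 7-12 PDC. The 6-month comparison is unaffected, and the 12-month PDC remains a valid measure of adherence over the whole first year.

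**What to change.** In section 20.0, replace the two overlapping outcomes with two that do not overlap, for both groups:

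- PDC for months 1-6 (about days 1-180)
- PDC for months 7-12 (about days 181-360)

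Apply the t-test and any adjusted regression to each, and define the PDC of at least 80% outcomes, with their chi-square tests and logistic models, on the same windows. Keep the 12-month PDC as an overall or descriptive measure, and state that it will not be interpreted as the post-call effect.

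Three definitions should be settled at the same time:

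- **Start date for controls.** Both windows run from the initial call, which controls do not receive. The current outcomes already need this date.
- **Number of follow-up calls.** Sections 6.2 and 7.3 give five, and section 9.3 in one place gives six. These must be reconciled. Under the longer schedule the last call falls at about the six-month boundary, so the start of the post-call window should be fixed against the reconciled schedule.
- **Supply that crosses the boundary.** State how days of supply dispensed in the first window and running into the second are counted.

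The cost is SAP wording and one additional PDC calculation from refill data already being collected. No new patients or data are needed. Making the change before outcome data are seen keeps the post-call comparison prespecified rather than post hoc.
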